9. BIOMARKER ANALYSIS

The biological marker analysis will be conducted on the Biomarker Analysis Set, defined in Section 3.1.7.

Serum hs-CRP, fecal calprotectin, and fecal lactoferrin will be listed and summarized for Cohort A Induction Study, Cohort B Induction Study, and Maintenance Study separately by treatment using descriptive statistics including baseline (or re-baseline) values, values at each postbaseline time point, change from baseline (or re-baseline) and percent change from baseline (or re-baseline) at each postbaseline time point. The definitions of baseline (or re-baseline) for each study are in Section 3.8.1.

Summaries of fecal calprotectin and serum hs-CRP for subjects who have baseline (or re-baseline) values satisfying the following criteria will also be provided for Cohort A Induction Study, Cohort B Induction study, and Maintenance Study:

- Fecal calprotectin $> 250 \mu\text{g/g}$
- Fecal calprotectin $\leq 250 \mu\text{g/g}$
- hs-CRP $> 3 \text{ mg/L}$
- hs-CRP $\leq 3 \text{ mg/L}$

Mean (Q1, Q3) of the observed change from baseline (or re-baseline) values for fecal calprotectin, fecal lactoferrin, and serum hs-CRP will be plotted by treatment and visit for Cohort A Induction Study, Cohort B Induction Study, and Maintenance Study separately as well.

11. SOFTWARE

SAS[®] Software Version 9.4 (SAS Institute Inc., Cary, NC, USA.) is to be used for all programming of tables, listings, and figures.

nQuery Advisor[®] Version 6.0 (Statistical Solutions, Cork, Ireland.) was used for sample size and power calculation.

12. SAP REVISION

Revision Date (DD MMM YYYY)	Section	Summary of Revision	Reason for Revision
Original Final Draft (07 September 2016)			
27 April 2018	1	Added key secondary objectives of establishing MCS remission (alternative definition) at Week 10 for Cohort A and B Induction Studies and at Week 58 for Maintenance Study	To align with Protocol Amendment 4
	3	Modified definition for Per-Protocol Analysis Sets	To better conduct Per-Protocol analysis
	3, 7	Added Cohorts A and B pooled safety summary	To support safety evaluation of study drug across Induction Studies
	3, 7	Clarified overall safety summaries only include adverse events and laboratory abnormalities including data collected across Cohort A Induction Study, Cohort B Induction Study and Maintenance Study	To support safety evaluation of study drug across Induction and Maintenance Studies
	5	Modified the list of variables to be summarized in baseline characteristic tables	To provide better characterization of the investigated patient populations
	7	Clarified AEs of interest to be summarized	To better address safety concerns
	7	Added summary of complete blood count-related laboratory evaluations	To better address safety concerns
	7	Removed shift relative to baseline tables for laboratory assessment including hematology and chemistry	To simplify the analysis
	Appendix 1	Update Schedule of Assessments	To align with Protocol Amendment 4
	Global	Administrative and editorial changes have been made throughout the SAP, where appropriate	Improve clarity and consistency

Revision Date (DD MMM YYYY)	Section	Summary of Revision	Reason for Revision
28 November 2018	3.5 and 6.1	Changed the testing strategy of efficacy endpoints of two filgotinib dose groups from separate to sequential testing with the proposed testing order	In response to comments from FDA
	4.2.2	Further specified details of adherence rate calculation	Improve clarity
	5.2	Added variables of baseline characteristics	To provide better characterization of subjects
	6.2.5	Added subgroup analysis regarding biologic treatment history for Maintenance Study	To better characterize the treatment efficacy profile of Maintenance Study
	7.1.8	Added subgroup summary of AEs and SAEs	In response to comments from FDA
	7.2.4	Added summary of shift change in selective laboratory tests	In response to comments from FDA
	9	Planned summary of additional PK parameters	due to data availability
08 April 2019	1.3	Power calculation revised according to the current alpha spending strategy	In response to comments from FDA
	3	Changed the testing strategy of efficacy endpoint of two filgotinib dose groups to sequentially rejective multiple test procedures	In response to comments from FDA
	Global	Administrative and editorial changes have been made throughout the SAP, where appropriate	Improve clarity and consistency

Revision Date (DD MMM YYYY)	Section	Summary of Revision	Reason for Revision
28 April 2020	3.2	For Maintenance Study summary, the subject grouping would not pool all placebo subjects into one group.	Placebo groups not pooled for the Maintenance study in response to comments from FDA on the integrated safety analysis SAP and also in recognition of different patient populations of filgotinib 200mg induced responders, filgotinib 100 mg induced responders, and placebo induced responders
	4.1, 4.2, 5.1 and 5.2	Added enrollment and disposition summary for Cohorts A and B combined.	To report overall patient population and disposition for filgotinib UC program
	4.1	Added “Per-Protocol Analysis Set”, “PK Analysis Set” and “Biomarker Analysis Set” into Maintenance Study disposition table.	To improve the completeness of the Maintenance Study disposition table.
	6.1 and 6.4	Added exploratory endpoints of EBS remission (alternative definition) at Week 10 for Induction Studies A and B and at Week 58 for Maintenance Study	In response to comments from FDA
	8.2.2 and 8.3	Removed PK parameters C_{last} , T_{last} , $t_{1/2}$, λ_z and V_{ss}/F ; removed listing of individual data on determination of the plasma half-life and corresponding correlation coefficient	To remove parameters that are less appropriate/informative to characterize the steady state PK
	Appendix	Removed Appendix 7 – Appendix 12 from previous SAP	Appendix 7 – Appendix 12 in the previous SAP were MSTs for AEI. As internal process has evolved and the AEI flags are included into the raw datasets, those appendixes have been removed from the SAP.
	Global	Administrative and editorial changes have been made throughout the SAP, where appropriate	Improve clarity and consistency

Appendix 1. Schedule of Assessments

Period	Screen	Treatment																			Follow-up	
Visit	1	2	3	4	5	6	7	8	9	10	11	12	13	14	15	16	17	18	19	20	PTx ^a	ET
Week		0	2	4	6	10	11	14	17	20	23	26	30	34	38	42	46	50	54	58		
Study Day	-30 to -1	1	15	29	43	71	78	99	120	141	162	183	211	239	267	295	323	351	379	407		
Visit Window			±3	±3	±3	±2	±3	±5	±5	±5	±5	±5	±5	±5	±5	±5	±5	±5	±5	±5	±3	±3
Written Informed Consent	X																					
Medical History & Demographics	X																					
Ulcerative Colitis Treatment History and disease extent	X																					
12-lead ECG	X					X						X									X	X ^b
Review of Inclusion/Exclusion Criteria	X	X																				
Complete Physical Exam ^c	X																					
Symptom directed physical exam ^c (as needed)		X	X	X	X	X	X	X		X		X		X		X		X		X	X	X
Vital Signs	X	X	X	X	X	X	X	X		X		X		X		X		X		X	X	X
Height	X																					
Weight	X	X	X	X	X	X		X		X		X		X		X		X		X	X	X
Adverse Events	X	X	X	X	X	X	X	X		X		X		X		X		X		X	X	X
Concomitant Medications	X	X	X	X	X	X	X	X		X		X		X		X		X		X	X	X

Period	Screen	Treatment																			Follow-up	
Visit	1	2	3	4	5	6	7	8	9	10	11	12	13	14	15	16	17	18	19	20	PTx ^a	ET
Week		0	2	4	6	10	11	14	17	20	23	26	30	34	38	42	46	50	54	58		
Study Day	-30 to -1	1	15	29	43	71	78	99	120	141	162	183	211	239	267	295	323	351	379	407		
Visit Window			±3	±3	±3	±2	±3	±5	±5	±5	±5	±5	±5	±5	±5	±5	±5	±5	±5	±5	±3	±3
Randomization		X					X															
Study Drug Dispensing		X		X			X	X		X		X		X		X		X				
Colonoscopy/Flexible Sigmoidoscopy with biopsy	X ^d						X														X	
Investigator Endoscopic Value (0,1,2, or 3) ^e	X						X														X	
Mayo Score (Partial) ^f		X	X	X	X		X	X		X		X		X		X		X				X
Mayo Score (Complete)	X						X														X	
eDiary instruction & review ^g	X	X	X	X	X	X	X	X		X		X		X		X		X			X	
Stool for C. diff toxin, pathogenic E. coli , Salmonella spp, Shigella spp, Campylobacter spp or Yersinia spp testing	X																					
Stool O&P ^h	X																					
Stool microbiome	X						X					X									X	
Fecal MMP-9	X						X					X									X	

Period	Screen	Treatment																			Follow-up	
Visit	1	2	3	4	5	6	7	8	9	10	11	12	13	14	15	16	17	18	19	20	PTx ^a	ET
Week		0	2	4	6	10	11	14	17	20	23	26	30	34	38	42	46	50	54	58		
Study Day	-30 to -1	1	15	29	43	71	78	99	120	141	162	183	211	239	267	295	323	351	379	407		
Visit Window			±3	±3	±3	±2	±3	±5	±5	±5	±5	±5	±5	±5	±5	±5	±5	±5	±5	±5	±3	±3
Fecal Lactoferrin, Calprotectin	X					X						X									X	
Urine drug screen ⁱ	X																					
Urinalysis	X	X				X															X	
Pregnancy Test ^j	X	X		X	X	X		X	X	X	X	X	X	X	X	X	X	X	X	X	X	X
TB ^k	X																					
Chest x-ray ^l	X																					
HBV, HCV, HIV screening ^m	X																					
HBV DNA monitoring (Japan) ⁿ				X	X	X		X	X	X	X	X	X	X	X	X	X	X	X	X	X	X
HBV monitoring (other regions) ⁿ						X				X				X				X			X	
Hematology	X	X	X	X	X	X		X		X		X		X		X		X		X	X	X
Chemistry	X	X	X	X	X	X		X		X		X		X		X		X		X	X	X
Lipid profile (fasting) ^o		X				X						X									X	X
CRP	X	X	X	X	X	X		X		X		X		X		X		X		X	X	X
Serum immunoglobulin		X		X		X						X									X	X

Period	Screen	Treatment																			Follow-up	
Visit	1	2	3	4	5	6	7	8	9	10	11	12	13	14	15	16	17	18	19	20	PTx ^a	ET
Week		0	2	4	6	10	11	14	17	20	23	26	30	34	38	42	46	50	54	58		
Study Day	-30 to -1	1	15	29	43	71	78	99	120	141	162	183	211	239	267	295	323	351	379	407		
Visit Window			±3	±3	±3	±2	±3	±5	±5	±5	±5	±5	±5	±5	±5	±5	±5	±5	±5	±5	±3	
Blood TCR/BCR repertoire samples ^p		X		X		X					X									X		
Plasma biomarker sample		X		X		X					X									X		
Serum biomarker sample		X		X		X					X									X		
Blood transcriptome sample		X		X		X					X									X		
PK collection (sparse) ^q				X		X					X									X		
vPBMC ^r		X		X		X					X									X		
PK substudy ^s				X																		
CCI																						
HRQoL Surveys ^u		X				X					X									X		
HCRU questionnaire		X	X	X	X	X	X	X		X		X		X		X		X		X		

- a The Post Treatment (PTx) visit should occur 30 days after the last dose of study drug. Only subjects who roll over into the LTE study (GS US 418 3899) will not complete PTx assessments.
- b For subjects who terminate prior to Week 10
- c A complete physical examination (PE) including, vital signs, body weight, and height will be performed at screening. (GU exam at investigator discretion). A symptom directed PE may be done as needed at other time points.
- d Diary data and other eligibility criteria should be reviewed prior to scheduling endoscopy. Perform the screening colonoscopy/flexible sigmoidoscopy within 2 weeks of Day 1 (Day 14 to -1). Subject should meet stool frequency and rectal bleeding requirements based on diary data prior to endoscopy performance.
- e The investigator (ie, local endoscopist) should enter in an endoscopic subscore (0, 1, 2, or 3) based on the Mayo Clinic Scoring System endoscopic scale (Protocol Appendix 4); this will be entitled the Investigator Endoscopic Value. The locally read score entered may not be used for eligibility or Mayo Clinic Score calculation purposes, and is not a substitute for the centrally read score, but is collected solely for exploratory purposes.

- f Includes all parts of the Mayo score except endoscopy
- g Subjects should begin filling out the eDiary the day after their initial screening visit and continue to fill it out throughout the remainder of the study.
- h Stool samples should be collected to rule out infectious causes when disease worsens.
- i Positive cocaine test disqualifies subject; positive amphetamines, barbiturates, benzodiazepines, and opioids require medical monitor review.
- j All females meeting the childbearing potential criteria must have a serum pregnancy testing at screening and a urine pregnancy test must be completed in clinic every 4 weeks at a minimum. If any pregnancy test is positive, study drug should be immediately interrupted and the subject should have a serum pregnancy test in clinic.
- k Proof of no active or untreated latent TB at screening. Subjects who are diagnosed with latent TB at screening must initiate an adequate course of prophylaxis as per local standard of care for a minimum of 4 weeks prior to randomization. Subject may initiate study drug dosing only after consultation with the medical monitor.
- l Chest x ray (views as per local guidelines) taken at screening or within the 3 months prior to screening (with the report or films available for investigator review) without evidence of active or latent TB infection
- m Hepatitis B surface Ag, surface Ab and core Ab, reflex HBV DNA, Hepatitis C Ab, reflex HCV RNA, HIV Ag/Ab, reflex HIV 1/2 Ab at Screening (Protocol Section 6.2.1).
- n In Japan, subjects with negative HBsAg, positive HBcAb and/or positive HBsAb at Screening require HBV DNA monitoring every 4 weeks in accordance with local guidelines (Protocol Section 6.2.1). In other regions, subjects with negative HBsAg and positive HBcAb require HBV DNA monitoring every 3 months in accordance with local guidelines (Protocol Section 6.2.1)
- o Fasting means no food or drink, except water, for 8 hours
- p TCR: T cell receptor; BCR: B cell receptor
- q This PK sample at Weeks 10 and 58 are collected at pre dose (within 2 hours prior to dosing). The PK sample at Week 4 is collected post dose (at least 30 minutes and up to 3 hours after study drug dosing). For this visit, it is preferred that study drug dosing is in clinic. The PK sample at Weeks 26 can be collected at any time without regard to dosing. For these visits, the time of dose taken on the day of and the dose taken prior to the PK sample being drawn will be noted in the eCRF.
- r vfpBMC collection at US and Canadian sites only.
- s Subjects who consent to optional PK substudy will have an additional plasma PK sample at any single visit from Week 2 and 10, collected pre dose and at 0.5, 1, 2, 3, 4 and 6 hours after supervised dosing in the clinic. For all visits with PK sampling, the time of dose taken prior to and on the day of visit will be noted in the eCRF
- t [REDACTED]
- u HRQoLs include SF 36, WPAI, EQ 5D, IBDQ.

Appendix 2. Biologics for UC Treatment

The drug names of biologics considered as UC treatment are listed below.

No.	Drug Class	Drug Name
1	TNF α antagonist	Adalimumab
2	TNF α antagonist	Golimumab
3	TNF α antagonist	Infliximab
4	TNF α antagonist	TNF α antagonist biosimilar (to adalimumab, golimumab, or infliximab)
5	Integrin receptor antagonist	Vedolizumab

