#### **Stratification Factors (Cohort B, Biologic-Experienced Induction Study)**

- Exposure to one biologic agent versus more than one biologic agent
- Concomitant use of oral, systemically absorbed corticosteroids (eg, prednisone) at Day 1, (Yes or No)
- Concomitant use of immunomodulators (eg, 6-MP, azathioprine, MTX) at Day 1, (Yes or No)

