#### **4.3.2. Exclusion Criteria, Cohort A ONLY**

Subjects who meet any of the following exclusion criteria are not to be enrolled in Cohort A Induction Study.

- 1) Prior use of any TNF $\alpha$  antagonist including (but not limited to) infliximab, adalimumab, golimumab, certolizumab, or biosimilar agents at any time
- 2) Prior or current use of vedolizumab at any time

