## 8.9. Sample Size

### 8.9.1. Induction Studies (Cohorts A and B)

The sample size was chosen to ensure that a clinically meaningful difference in EBS remission rate at Week 10 could be detected when comparing filgotinib to placebo within each Induction Study.

A sample size of 130 subjects in the placebo group and 260 subjects in each filgotinib dose group (n = 650 total per cohort) will provide 90% power for each filgotinib dose group comparison to placebo at a 2-sided 0.025 significance level to detect a treatment difference in EBS remission rate of 15% (25% on filgotinib and 10% on placebo).

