3.1.3. Per-Protocol Analysis Sets

The Per-Protocol (PP) Analysis Set for each Induction Study (Cohort A Induction Study and Cohort B Induction Study) includes subjects in the respective FAS who meet the following criteria:

- Met the following key eligibility criteria:

Documented diagnosis of UC of at least 6 months AND with a minimum disease extent of 15 cm from the anal verge. Documentation should include endoscopic and histopathologic evidence of UC as follows:

- The criteria for documentation of UC based on endoscopy will be medical record documentation, or an ileocolonoscopy (full colonoscopy with the intubation of the terminal ileum) report dated ≥ 6 months before enrollment, which shows features consistent with UC, determined by the procedure performing physician
- The criteria for documentation of UC based on histopathology will be medical record documentation of or a histopathology report indicating features consistent with UC as determined by the pathologist

Moderately to severely active UC as determined by a centrally read endoscopy score ≥ 2 , a rectal bleeding score ≥ 1 , a stool frequency score ≥ 1 , and PGA of ≥ 2 as determined by the Mayo clinic scoring system with endoscopy occurring during screening; total score must be between 6 and 12, inclusive.

- Dosed at least 80% of both study drugs (filgotinib and PTM) while on-treatment (see Section 4.2.2) for the Induction Study
- Either had sufficient data to evaluate EBS remission at Week 10, or met treatment failure criteria for Week 10 EBS remission outcome
- Never exposed to any biologics listed in Appendix 2 for Cohort A Induction Study, or exposed to at least 1 of the biologics listed in Appendix 2 for Cohort B Induction Study

The PP Analysis Set for the Maintenance Study includes subjects in the FAS who meet the following criteria:

- Met the key eligibility criteria from Induction Study as stated above
- Dosed at least 80% of each study drug type while on-treatment (see Section 4.2.2) for Maintenance Study
- Met one of following 3 categories:

Had sufficient data to evaluate EBS remission outcome at Week 58, or

Met treatment failure criteria for Week 58 EBS remission outcome, or

Discontinued study drug due to protocol-specified disease worsening criterion

The PP Analysis Set is the secondary analysis set for efficacy analyses.

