3.5. Multiple Comparisons

The graphical approach {Bretz 2009} to sequentially rejective multiple test procedures will be used to control a family-wise type I error rate (FWER) at 5% (ie, $\alpha = 0.05$) for each individual study (Cohort A Induction Study, Cohort B Induction Study, and Maintenance Study). This procedure strongly protects the FWER on all the primary and key secondary endpoints.

Induction Studies (Cohort A Induction Study and Cohort B Induction Study)

For each individual study (Cohort A Induction Study, Cohort B Induction Study, and Maintenance Study), a Bonferroni approach with equal alpha allocation of 0.025 (2-sided) to each filgotinib dose group comparison with placebo will be used to control the overall study-wide type I error rate at 0.05 within each study. To protect the integrity of the study due to the unblinded interim futility analysis planned for each induction study (Cohort A Induction Study and Cohort B Induction Study), an alpha of 0.00001 will be spent for each filgotinib dose group comparison to placebo within each induction study. As a result, a nominal p-value of less than 0.02499 (2-sided) will be needed to declare statistical significance for the final primary analysis of each filgotinib dose group when compared to placebo to control the study-wise type I error rate at 0.05. If one filgotinib dose group is discontinued for futility at the interim futility analysis, the overall alpha error rate stays unchanged at a 2-sided 0.02499 level for the continuing filgotinib dose group at the primary analysis.

The hypotheses to be tested for the induction studies are outlined below.

The primary null hypotheses to be tested:

- H1: The EBS remission rate in the filgotinib 200 mg group is equal to the EBS remission rate in the placebo group at Week 10
- H2: The EBS remission rate in the filgotinib 100 mg group is equal to the EBS remission rate in the placebo group at Week 10

[figure not shown]
The key secondary null hypotheses to be tested:

- H3: The MCS remission rate in the filgotinib 200 mg group is equal to the MCS remission rate in the placebo group at Week 10
- H4: The MCS remission rate in the filgotinib 100 mg group is equal to the MCS remission rate in the placebo group at Week 10
- H5: The endoscopic subscore of 0 rate in the filgotinib 200 mg group is equal to the endoscopic subscore of 0 rate in the placebo group at Week 10

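### SAP Appendix 2 leaves out certolizumab, so the per-protocol rule misclassifies its users, and a few Cohort B subjects may be analysed in a different exposure stratum from the one randomised

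*SAP*

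**What the plan says.** **Randomisation.** The protocol stratifies Cohort B by "Exposure to one biologic agent versus more than one biologic agent". No drug list is attached there, in protocol Sections 3.3 and 6.1, or in the restatement in SAP Section 1.2.1.

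**Analysis.** The primary CMH test (SAP Section 6.2.3), the missing-data summaries (6.2.4.3) and the subgroups (6.2.5) count only drugs in Appendix 2, cut as at most one against more than one. SAP Sections 3.3 and 6.2.3 take the stratum from the clinical database when it differs from the IWRS.

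**The list.** Appendix 2 is introduced by "The drug names of biologics considered as UC treatment are listed below". It contains adalimumab, golimumab, infliximab, biosimilars of those three, and vedolizumab.

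**Eligibility.** Protocol Section 4.3.2 excludes from Cohort A anyone with prior use of a TNFα antagonist, including "infliximab, adalimumab, golimumab, certolizumab, or biosimilar agents at any time". Protocol Section 4.4.1 admits to Cohort B a subject with a history of intolerance to any TNFα antagonist.

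**Per-protocol set.** SAP Section 3.1.3 requires "Never exposed to any biologics listed in Appendix 2 for Cohort A Induction Study" and, for Cohort B, exposure to at least one drug on the same list.

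**The concern.** The per-protocol exposure condition is the only part of that definition that checks biologic status; the key eligibility criteria restated beside it cover diagnosis and disease activity. If its list is shorter than the protocol's, the set contradicts the eligibility rule it is meant to enforce. The per-protocol analysis is the one SAP Section 6.2.4.1 uses to judge the impact of study conduct.

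The second issue is that an analysis factor should describe the same groups as the randomisation factor. A restricted count in the CMH test and an unrestricted one at randomisation would put some subjects in different strata in the Cohort B primary test and subgroup analysis. SAP Section 6.6, which lists changes from the protocol's efficacy analyses, does not mention a restriction.

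**Working it through.** **1. The plan's power figure.** Protocol Section 8.9.1 gives the inputs: "A sample size of 130 subjects in the placebo group and 260 subjects in each filgotinib dose group", rates of "25% on filgotinib and 10% on placebo", and a design that "will provide 90% power for each filgotinib dose group comparison to placebo at a 2-sided 0.025 significance level".

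- Pooled rate: (130 × 0.10 + 260 × 0.25) / 390 = 78 / 390 = 0.20.
- SE under the null: √[0.20 × 0.80 × (1/130 + 1/260)] = 0.04297.
- SE under the alternative: √[0.10 × 0.90/130 + 0.25 × 0.75/260] = 0.03760.
- Without continuity correction: power = Φ[(0.15 − 2.2414 × 0.04297) / 0.03760] = Φ(1.428) = 92.3%. For 90% power, 121 placebo subjects are needed.
- With continuity correction: 131 placebo subjects are needed for 90% power. The largest power, in steps of 0.1 points, that needs no more than 130 is 89.8%.

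The stated 90% reproduces with the correction. It does not depend on the drug list.

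**2. Per-protocol status.** Two profiles, read against the protocol and against SAP Section 3.1.3:

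| Subject | Protocol | Per-protocol exposure condition |
|---|---|---|
| Prior certolizumab, entered in Cohort A | Breaches Section 4.3.2 | Passes: no listed drug |
| Certolizumab the only biologic, entered Cohort B through intolerance | Eligible under Section 4.4.1 | Fails: no listed drug |

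Both results are the reverse of what the protocol implies. The inadequate-response and recurrence routes into Cohort B name only infliximab, adalimumab and golimumab, so intolerance is the clear route for the second subject.

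**3. Cohort B stratum.** Certolizumab, natalizumab and ustekinumab all appear in protocol Table 5-1 with a washout before screening, so prior use is possible.

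| Prior biologics | Protocol wording, taken literally | SAP CMH factor |
|---|---|---|
| One listed only | one | at most one |
| One unlisted only (for example certolizumab) | one | at most one |
| Two listed | more than one | more than one |
| One listed and one unlisted | more than one | at most one |

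A stratum changes only when removing unlisted drugs takes the count from above one to one or zero.

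**4. How many.** The documents give no count. As an assumption with no source in them, 1% to 5% of the 390 subjects in one dose comparison (130 + 260) would be 0.01 × 390 = 3.9 to 0.05 × 390 = 19.5, or about 4 to 20.

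**5. Effect on the primary test.** The stratified CMH test was simulated with 40,000 runs per setting and the SAP Section 3.5 threshold: "a nominal p-value of less than 0.02499 (2-sided) will be needed to declare statistical significance for the final primary analysis". The assumptions, none of them in the documents, were:

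- 40% or 60% of Cohort B truly in the higher-exposure stratum;
- remission 8 points lower in that stratum, with overall rates kept at 10% and 25% (10% in both arms under the null);
- 0%, 5%, 10%, 20% or 50% of the higher stratum analysed in the lower one, at the same rate in each arm;
- 130:260 allocation within each stratum, with exposure the only stratifier.

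At 40%, the higher stratum holds 0.40 × 390 = 156 subjects, so moving half moves 78. At 60% it holds 234, and half is 117. Both far exceed the 4 to 20 assumed in step 4.

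Type I error ranged from 0.0229 to 0.0258 and power from 92.9% to 93.2%. Neither showed a trend with the proportion moved. The Monte Carlo standard error of the type I error is about √(0.025 × 0.975 / 40,000) = 0.0008, so the spread is about what simulation noise gives.

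**The case against.** The strongest reply is that the short list may be deliberate and may match what the sites used. The title of Appendix 2 limits it to biologics for UC treatment. Its drugs are those with induction regimens in protocol Section 4.4.1, and protocol Section 1.1 describes ustekinumab as still in Phase 3 testing. Neither document says which drugs the IWRS counted. This stands: a mismatch with the stratum actually randomised is possible, not shown. It does not rescue the per-protocol rule, because protocol Section 4.3.2 names certolizumab.

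Part of the problem would also surface elsewhere. SAP Section 4.1 summarises and lists subjects whose IWRS and database strata differ, and Section 4.3 lists eligibility failures, so a certolizumab user in Cohort A should be visible there. That is reporting; it does not correct membership of the per-protocol set.

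A reader might also infer that ustekinumab and natalizumab belong in the per-protocol rule. The documents do not support this for Cohort A. The exclusions in protocol Section 4.3.2 cover TNFα antagonists and vedolizumab only. Adding the other two would remove subjects the protocol allows.

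**Conclusion.** The point holds and is minor. The firm part is certolizumab: its omission makes the per-protocol rule wrong in both directions, in a set the SAP calls secondary.

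The conditional part is the Cohort B stratum. A reader might infer that Cohort B as a whole is analysed in the wrong strata, or that its primary test is unsound. The documents do not support either reading. Only subjects with one listed and at least one unlisted biologic could move, and only if the IWRS counted the unlisted drug. Exposure is a baseline variable, the reported risk difference is unstratified (SAP Section 6.2.3), and the simulation found no material change in type I error or power.

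That last result assumes equal movement across arms and the same allocation in every stratum. Neither need hold for 200 mg against placebo in Cohort B. US and Korea males who are not dual refractory can receive placebo but not 200 mg (SAP Section 6.2.4.4), so the grouping of exposure could matter somewhat more there. The simulation does not cover that case.

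**What to change.** 1. Add certolizumab to Appendix 2, worded as any TNFα antagonist including biosimilars. This corrects the per-protocol rule for both cohorts. Do not add ustekinumab, natalizumab or a general category of other biologics to the Cohort A per-protocol rule.
2. State which drugs were counted when the IWRS exposure category was assigned. Define the Cohort B CMH exposure factor as that one against more-than-one category, or keep the current factor and add a CMH test on the randomised category to SAP Section 6.2.4.
3. If counting only Appendix 2 drugs is intended, say so and give the reason in SAP Section 6.6.

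The cost is one table row, two or three sentences and at most one extra CMH run per dose. UC treatment history is already collected at screening. If the SAP is already final, its Section 1 provides for recording such changes in the clinical study report.
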